3.4.1 Phase 2 Efficacy Endpoints – Month 6 Analysis

3.4.1.1 Phase 2 Primary Efficacy Endpoint in the US (Secondary Endpoint Outside the US)

The primary efficacy endpoint in the US (secondary outside the US) is symptom-based clinical response assessed by MACrO₂ PRO between baseline and Month 3 and baseline and Month 6. While summary results for both of these visits will be generated in parallel, the Month 6 visit will be considered of primary interest with the Month 3 visit considered supportive. The Estimand corresponding to the primary endpoint is defined with the following five attributes:

1. Population: Randomized patients with MAC culture-positive Pre-Study and Screening respiratory specimens
2. Treatment: Epetraborole oral tablets 500 mg (two 250 mg oral tablets) QD + OBR or placebo oral tablets QD matched to epetraborole dosage + OBR
3. Variable: MACrO₂ PRO response rate at Month 3 and Month 6. MACrO₂ PRO response at the given time point is defined as improvement of ≥ 1 grade in the key symptom with no worsening of other symptoms compared with baseline MACrO₂ PRO assessment. The baseline MACrO₂ PRO assessment is defined as the last assessment prior to the first dose of study drug.
4. Intercurrent events:
 - a. New, additional non-study-specific, antimycobacterial therapy that is potentially effective against MAC for reasons other than clinical failure of study drug: data collected after such therapy will not be used and patients will be classified as a clinical failure for MACrO₂ PRO response (composite strategy)
 - b. Surgery for MAC lung disease for reasons other than clinical failure of study drug: data collected after such surgery will not be used and patients will be classified as a clinical failure for MACrO₂ PRO response (composite strategy)
 - c. Permitted medications/interventions or prohibited medications/interventions other than those described in bullets a and b: MACrO₂ PRO data collected after permitted or other prohibited medications/interventions administration will be used as recorded (treatment policy strategy)
 - d. Inadequate compliance: patient data will be used as recorded (treatment policy strategy)
5. Population-level summary: Difference between epetraborole + OBR and placebo + OBR in response rate in MACrO₂ PRO assessment at Month 3 and Month 6.

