3.4.3 Phase 3 Efficacy Endpoints

3.4.3.1 Phase 3 Primary Efficacy Endpoint in the US (Key Secondary Endpoint Outside the US)

The primary efficacy endpoint in the US (key secondary outside the US) is change from baseline to Month 6 in QOL-B respiratory domain score. The Estimand corresponding to the primary endpoint is defined with the following five attributes:

1. Population: Patients with MAC culture-positive Pre-Study and Screening respiratory specimens
2. Treatment: Epetraborole oral tablets 500 mg (two 250 mg oral tablets) QD + OBR or placebo oral tablets QD matched to epetraborole dosage + OBR
3. Variable: Change from baseline to Month 6 in QOL-B respiratory domain score. QOL-B respiratory domain score is measured on a scale from 0 to 100 (with higher scores indicating better health-related quality of life). The baseline QOL-B respiratory domain score assessment is defined as the last entry recorded or updated by the patient on or prior to the first dose of study drug + 1 day (ePRO-specified close of window to further entry to patients).
4. Intercurrent events:
 - a. New, additional non-study-specific, antimycobacterial therapy that is potentially effective against MAC for reasons other than clinical failure of study drug: data collected after such therapy will be set to the last available score from a visit prior to the start of therapy (composite strategy)
 - b. Surgery for MAC lung disease for reasons other than clinical failure of study drug: data collected after such surgery will not be used and results will be set to the last available score from a visit prior to surgery (composite strategy)
 - c. Permitted medications/interventions or prohibited medications/interventions other than those described in bullets a and b: QOL-B respiratory domain data collected after permitted or other prohibited medications/interventions administration will be used as recorded (treatment policy strategy)
 - d. Inadequate compliance: patient data will be used as recorded (treatment policy strategy)

5. Population-level summary: Difference between epetraborole + OBR and placebo + OBR in least squares mean change from baseline to Month 6 in QOL-B respiratory domain score.

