2. Treatment: Epetraborole oral tablets 500 mg (two 250 mg oral tablets) QD + OBR or placebo oral tablets QD matched to epetraborole dosage + OBR
3. Variable: Sputum conversion rate is defined as proportion of patients having culture conversion based on 3 consecutive monthly negative sputum cultures for MAC by Month 6
4. Intercurrent events:
 - a. New, additional non-study-specific, antimycobacterial therapy that is potentially effective against MAC for reasons other than clinical failure of study drug: data collected after such therapy will not be used and patients will be classified as a failure for microbiological response (composite strategy)
 - b. Surgery for MAC lung disease for reasons other than clinical failure of study drug: data collected after such surgery will not be used and patients will be classified as a failure for microbiological response (composite strategy)
 - c. Permitted medications/interventions and or prohibited medications/interventions other than those described in bullets a and b: microbiological response data collected after permitted or other prohibited medications/interventions administration will be used as recorded (treatment policy strategy)
 - d. Inadequate compliance: patient data will be used as recorded (treatment policy strategy)

5. Population-level summary: Difference between epetraborole + OBR and placebo + OBR in sputum conversion rate by Month 6.

“Microbiological response” is defined as sputum culture conversion based on 3 consecutive monthly negative sputum cultures for MAC by Month 6. By-patient microbiological response will be presented for the Micro-ITT Population by Month 6. Descriptive statistics (n, %) will be presented by treatment group, along with the treatment difference (i.e. epetraborole + OBR response percentage minus placebo + OBR response percentage), associated 95% confidence interval and p-value, calculated using the method of Miettinen and Nurminen, both including (primary analysis) and excluding (sensitivity analysis) stratification by baseline ALIS use and the presence or absence of any fibrocavitary disease.

3.4.3.3 *Secondary Efficacy Endpoints*

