Descriptive statistics of both the reported scores and change from baseline (for continuous scores only) will be reported by visit (monthly through Month 6) for scores for all PROs collected in the study (QOL-B domain scores, MACrO₂ total scaled score, NTM Symptoms Module, SGRQ-C, PGIS, PGIC, CGIS, CGIC, and Meaningful Change Question) based on the Micro-ITT Populations. Change from baseline score at Month 3 and Month 6 of selected continuous PROs including QOL-B respiratory domain score (Month 3 only, as Month 6 is the primary efficacy analysis), MACrO₂ total scaled score, NTM Symptoms Module domain score, and SGRQ-C total score will be analyzed using an analysis of covariance (ANCOVA) model, including baseline score, treatment and stratification factors (baseline ALIS use and presence or absence of any fibrocavitary disease) as covariates. Least squares means, 95% confidence intervals, and p-values of the treatment comparison will be presented for both Micro-ITT and PP populations. Intercurrent events will be handled following the same rules as for the primary efficacy analysis.

Clinical response as defined above for the MACrO₂ PRO as well as for each additional PRO measure according to pre-defined response thresholds relative to baseline will be examined monthly through Month 6. MACrO₂ original responder is defined as improvement of ≥ 1 grade in the key symptom with no worsening of other symptoms. Response in QOL-B respiratory domain score is defined as an improvement

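### The Phase 3 QOL-B primary estimand calls a carry-forward rule composite, and no planned analysis counts the event as an unfavourable outcome

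*SAP*

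**What the plan says.** SAP 3.4.3.1 defines the outcome plainly: "Variable: Change from baseline to Month 6 in QOL-B respiratory domain score", on a 0-100 scale where higher is better. It then lists four intercurrent events.

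- **Item 4a** (added antimycobacterial therapy potentially active against MAC): "data collected after such therapy will be set to the last available score from a visit prior to the start of therapy (composite strategy".
- **Item 4b** ("Surgery for MAC lung disease for reasons other than clinical failure of study drug"): "results will be set to the last available score from a visit prior to surgery (composite strategy". The same limit on the reason for the event applies in 4a.
- **Item 4c** ("Permitted medications/interventions or prohibited medications/interventions other than those described in bullets a and b"): data used as recorded, treatment policy.
- **Item 4d** (poor compliance): data used as recorded, treatment policy.

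The analysis text in 3.4.3.1 puts the carried values into the primary ANCOVA and refers to items 4a-b as imputation rules. For the other continuous PRO scores, including the MACrO₂ total scaled score, SAP 3.4.3.3 says: "Intercurrent events will be handled following the same rules as for the primary efficacy analysis".

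For Phase 3 culture conversion, SAP 3.4.3.2 item 4a reads: "data collected after such therapy will not be used and patients will be classified as a failure for microbiological response (composite strategy".

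**The concern.** A composite strategy builds the intercurrent event into the outcome, so having the event determines or worsens the patient's result. Items 4a-b do not do this. They replace the Month 6 score with an earlier one and analyse it as though it had been observed at Month 6. A patient who improved and then had the event keeps the whole improvement.

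A reader of the estimand therefore cannot tell which treatment effect is claimed. The label says that the event counts as part of the outcome; the rule says that the event is ignored and time is stopped just before it. The first two endpoints in the US testing order (SAP 3.4) use this rule. The third, culture conversion, treats the identically worded event as failure.

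**Working it through.** **1. The same label, side by side**

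| Place in SAP | Endpoint | Label in 4a-b | What happens to the patient |
|---|---|---|---|
| 3.4.1.1 | Phase 2 MACrO₂ response | composite | "patients will be classified as a clinical failure for MACrO₂ PRO response (composite strategy" |
| 3.4.1.2 | Phase 2 culture conversion | composite | failure |
| 3.4.3.2 | Phase 3 culture conversion | composite | failure |
| 3.4.3.1 | Phase 3 QOL-B change | composite | last pre-event score carried forward |

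Only the last row leaves the event out of the outcome.

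**2. One patient under the rule**

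Take a baseline score of 50, a Month 3 score of 61.1 and added therapy in Month 4. The Month 6 change entered is 61.1 − 50 = +11.1, equal to the second QOL-B response threshold in SAP 3.4.3.3. On the wording of 3.4.3.2 the same event makes the patient a failure for culture conversion. The rule works both ways: a last pre-event score of 45 would give 45 − 50 = −5, and if only the baseline score precedes the event the change is 0.

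**3. Does any planned analysis supply the composite?**

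- Sensitivity analysis 1 only drops the stratification factors.
- Sensitivity analyses 2 and 3 switch to treatment policy.
- The Per-Protocol run removes patients rather than scoring the event. Protocol 5.8.3 excludes anyone who received prohibited therapy.
- The exploratory MMRM (SAP 3.4.3.4) states no rule for these events.
- The responder analyses in SAP 3.4.3.3 count missing results as failures but do not name this event.

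None of them makes the event an unfavourable outcome for QOL-B or the MACrO₂ total score.

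**4. Size**

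The plan has no figure of its own to reproduce. The sample size in SAP 2.2.7 rests on response rates of 30% v 10%, and the documents give no event rate, QOL-B standard deviation or expected QOL-B effect. Everything below is assumption.

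As reference, take a composite that allows a change no better than 0. Carried losses are then identical under both rules, and only carried gains differ. With event share f, and g the mean carried gain among event patients (losses counted as 0):

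- shift in an arm mean = f × g
- shift in the treatment difference = f_E × g_E − f_P × g_P (E epetraborole, P placebo)

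| f_E | f_P | g_E | g_P | Shift in difference (points) |
|---|---|---|---|---|
| 5% | 5% | 8 | 8 | 0.40 − 0.40 = 0 |
| 10% | 5% | 5 | 5 | 0.50 − 0.25 = +0.25 |
| 10% | 5% | 8 | 8 | 0.80 − 0.40 = +0.40 |
| 10% | 5% | 11.1 | 0 | 1.11 − 0 = +1.11 |
| 20% | 10% | 11.1 | 11.1 | 2.22 − 1.11 = +1.11 |
| 5% | 10% | 8 | 8 | 0.40 − 0.80 = −0.40 |
| 10% | 20% | 11.1 | 11.1 | 1.11 − 2.22 = −1.11 |

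At event shares of 2-5% and gains of 8-11.1, the shift in one arm's mean is 0.02 × 8 = 0.16 to 0.05 × 11.1 = 0.56 points, before the other arm's shift is subtracted. The 1.11 ceiling belongs to these scenarios, not to the rule. A 20% event share with a gain of 11.1 in one arm and no gain in the other would give 2.22.

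For scale, assume a standard deviation of 15-25 and the planned 124 v 62 patients. The standard error of the difference is SD × √(1/124 + 1/62) = 2.33 to 3.89. It would be larger with fewer patients, which is likely because the trial was terminated early.

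**The case against.** The best defence has four parts.

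**Scope.** Items 4a-b exclude events caused by failure of study drug. SAP 3.3.6 uses similar wording for MAC-active antibiotics given for non-MAC infections, so 4a may largely capture patients whose later scores are contaminated rather than patients doing badly. Using the last clean score is then a defensible choice. This stands as an argument for carry-forward, but the SAP does not make it. It also does not explain why the same event is failure in 3.4.3.2.

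**Rule and analysis agree.** A reader might infer that the written rule is never analysed. That is not so: the primary ANCOVA applies items 4a-b as written. What is never estimated is the strategy that the label declares.

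**No natural failure value.** A 0-100 change score has none, so any composite value is a choice. This is true, and it is why the value needs prespecifying. A fixed unfavourable value is also a single assigned number, so the uncertainty ignored by single imputation is not a reason to prefer one option over the other.

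**Events should be few and checks exist.** Anticipated new antimycobacterial therapy and planned lung surgery are exclusions (Protocol 4.2), and the background regimen is largely fixed (Protocol 5.7.2). Sensitivity analyses 2-3 test dependence on carry-forward where Month 6 scores exist. That check could be thin: Protocol 5.7.2 stops study drug when rescue therapy for the index infection is added and then names only the EOT and LFU assessments, so a Month 6 score may be absent. How far those patients overlap with item 4a is uncertain.

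**Conclusion.** The point holds as an inconsistency in the primary estimand. Items 4a-b carry a score forward under a composite label, the label means failure everywhere else that the SAP uses it, and no planned analysis makes the event an unfavourable outcome for QOL-B or the MACrO₂ total score. It is more than wording, because a carried gain counts in full as a Month 6 change. It should be corrected, but it does not by itself undermine the primary analysis.

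Two stronger readings are tempting and are not supported.

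- **That the rule favours epetraborole.** Losses are carried as well as gains, and the documents give no event rates or trajectories by arm. The direction is unknown: zero with equal rates and gains, and within about ±1.1 points in the tabulated scenarios, against an 8-point threshold.
- **That patients rescued for failing treatment enter as improvers through carry-forward.** Items 4a-b exclude those events. On the wording of 4c their data would be used as recorded, which is a separate gap: the SAP does not say that this is intended.

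**What to change.** Before Phase 3 unblinding, make label and rule agree in SAP 3.4.3.1 items 4a-b, and in 3.4.3.3 for the MACrO₂ total scaled score. Either of two routes would do.

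1. **Implement a composite.** For example, set Month 6 to the worse of the baseline score and the last pre-event score, so that the change is no better than 0. Respect each scale's direction: worse is lower for QOL-B and higher for the MACrO₂ total score. Another prespecified unfavourable value would also serve. Keep carry-forward as a sensitivity analysis under its own name.
2. **Keep carry-forward.** Relabel it, justify it, and add the composite as a prespecified sensitivity analysis for both scores.

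Under either route, state explicitly how therapy or surgery given because of clinical failure is handled in the analysis, rather than leaving it to fall under 4c.

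The cost is SAP wording and one small derivation, with no new data. Arm means may come out slightly less favourable under the composite. Left until after Phase 3 unblinding, the change would have to be reported as a deviation (SAP section 1).

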7.5.5. Patient-Reported Outcome Measures

An electronic PRO system will be used during the study to allow patients to complete the study questionnaires.

In both the Phase 2 and Phase 3 parts of the study, each patient will complete the following PRO measures:

- MACrO₂
- QOL-B
- NTM Symptoms Module
- SGRQ-C
- Global assessment scales (Patient Global Impression of Severity [PGIS] and Patient Global Impression of Change [PGIC])

The Investigator will complete the Clinician Global Impression of Severity (CGIS) and Clinician Global Impression of Change (CGIC).

The PROs will be completed at the time points specified in the Schedule of Assessments ([Appendix A](#)). On Day 1, PROs should be completed prior to study drug administration, and will serve as the baseline assessment for comparison to on-treatment assessments. The MACrO₂, QOL-B, NTM Symptoms Module, SGRQ-C, and PGIS will be completed twice before the first

dose of study drug (ie, once between Days -14 and -7 and on Day 1 prior to study drug administration) to assess test-retest reliability. The MACrO₂ and PGIS will be completed at additional time points to further assess test-retest reliability. For patients whose EOT Visit coincides with the Month 3 or Month 6 visit, the MACrO₂ and PGIS will be completed 1 week (+1 day) after the EOT Visit. PRO test-retest reliability will be assessed in Phase 2 and may be analyzed in Phase 3 if deemed necessary.

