APPENDIX A. SCHEDULES OF ASSESSMENTS

Table 3: Schedule of Assessments: Screening through Month 6 (Phases 2 and 3)

	Month	Screening		Treatment Period								
		D-56 to -15	D-14 to -7	Randomization	1 ^a	2 ^a	3 ^a	3+1w	4 ^a	5 ^a	6 ^b	6+1w
				D1	D29 ±7d	D57 ±7d	D85 ±7d	1w (+1d) after M3	D113 ±7d	D141 ±7d	D169 ±7d	1w (+1d) after M6
Tests/Exams	Study Day/Visit Window ^c											
	Informed consent ^d		X									
	Inclusion/exclusion criteria		X ^e									
	Demographic information		X									
	Medical/surgical history		X	X	X							
	Physical examination ^f		X		X	X	X	X	X	X	X	
	Vital signs, weight ^g		X		X	X	X	X	X	X	X	
	Height, BMI ^g		X									
	12-lead ECG ^h		X		X		X		X		X	
Laboratory	Chest CT (non-contrast) ⁱ		X								X	
	Chemistry/Hematology ^j		X ^e		X ^k	X	X	X		X	X	X
	Urinalysis ^h		X		X ^k		X		X		X	
	Serum pregnancy test (FOCP only) ^h		X		X ^k							
	CrCl calculation ^l		X									
	ADH genotyping ^m				X							
	Sputum collection ⁿ		X			X	X	X		X	X	X
	Plasma PK sampling ^o				X	X						
PROs	MACrO ₂ PRO ^{p,q}			X ^r	X ^s	Weekly		X ^s	Weekly		X ^t	
	QOL-B, NTM Module, SGRQ-C ^p			X ^s	X ^s	X	X	X	X	X	X	
	PGIS ^p			X ^s	X ^s	X	X	X	X ^t	X	X	X
	PGIC ^p					X	X	X		X	X	X
	Meaningful Change Question ^t					X	X	X		X	X	X
	CGIS ^u				X	X	X	X		X	X	X
	CGIC ^u					X	X	X		X	X	X
	Qualitative Embedded Interview											X ^v
	Randomization				X							
	OBR administration ^w		X	X	X							
	Study drug administration				Daily ^x							
	Prior/concomitant medications		X	X	X	X	X	X		X	X	X
	Adverse events ^y		X	X	X	X	X	X		X	X	X

Note: See [Table 4](#) for Months 7-16, EOT/ET, and LFU assessments.

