2.2 Study Design

2.2.1 Overview

Refer to Protocol Section 3.1 Summary of Study Design for full details of the study overview.

Briefly, this is a pivotal Phase 2/3, double-blind, placebo-controlled study of eptraborole + OBR versus placebo + OBR in patients with treatment-refractory MAC lung disease. This study will enroll adult patients with treatment-refractory MAC lung disease who meet all eligibility criteria.

This study features a sequential Phase 2/3 approach with an initial Phase 2 assessment of clinical responses (based on clinical symptoms and/or functional assessments), microbiological responses, safety, and PK associated with oral eptraborole, prior to the superiority analysis of oral eptraborole versus placebo in the Phase 3 part of the study.

In both the Phase 2 and Phase 3 parts of the study, each patient will complete multiple PRO measures including MACrO₂, QOL-B, NTM Symptoms Module, SGRQ-C, and global patient and clinician assessment scales (Patient Global Impression of Severity [PGIS], Patient Global Impression of Change [PGIC], Clinician Global Impression of Severity [CGIS], Clinician Global Impression of Change [CGIC]), and Meaningful Change Question (to be answered after each completion of the PGIC). An electronic PRO system will be used during the study to allow patients to complete the study questionnaires electronically.

The MACrO₂ PRO will be completed twice before the first dose of study drug to assess test-retest reliability (within 1 to 2 weeks prior to randomization, and on randomization day prior to study drug administration) and once weekly for the first 6 months of the study; other PROs and global assessment scales will be completed at baseline and once monthly for the first 6 months of the study. The QOL-B, NTM Symptoms Module, SGRQ-C, and PGIS will also be completed during Screening for test-retest reliability assessment. The PGIC, CGIC, and Meaningful Change Question will not be completed at baseline. After Month 6, all PROs will be completed every 3 months (84 days \pm 7 days), at End of Therapy (EOT), and at Late Follow Up (LFU). Sputum samples for microbiological assessments will be collected during the Screening period, once monthly for the first 6 months of the study, and then every 3 months (84 days \pm 7 days), at EOT, and at LFU.

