QOL-B respiratory domain scores are measured on a scale from 0 to 100 (with higher scores indicating better health-related quality of life). QOL-B respiratory domain scores will be summarized by visit in the Micro-ITT Population. Descriptive statistics of both the reported QOL-B respiratory domain scores and change from baseline will be reported by visit (monthly through Month 6). Change from baseline to Month 6 in QOL-B respiratory domain score will be analyzed using an analysis of covariance (ANCOVA) model, including baseline score, treatment and either including (primary analysis) or excluding (sensitivity analysis 1) stratification factors of baseline ALIS use and the presence or absence of any fibrocavitary disease as covariates. Least squares means, 95% confidence intervals, and p-values of the treatment comparison will be presented for both the Micro-ITT (primary) and PP (sensitivity) populations.

Patients who fail to provide a complete QOL-B respiratory domain score at both baseline and Month 6 will be excluded from the analysis and considered unbiased under the missing at random (MAR) assumption, with the exception of patients experiencing intercurrent events, which will be accounted for following the imputation rules above. However, in an additional pair of sensitivity analyses, the primary efficacy analysis will be repeated as described above, but applying a treatment policy strategy in which results for patients with new, additional non-study-specific, antimycobacterial therapy that is potentially effective against MAC, or surgery for MAC lung disease, for reasons other than clinical failure of study drug, will be used as recorded. These models will be run using the ANCOVA model as described above, including baseline score, treatment and either including (sensitivity analysis 2) or excluding (sensitivity analysis 3) stratification factors of baseline ALIS use and the presence or absence of any fibrocavitary disease as covariates.

3.4.3.2 Phase 3 Primary Efficacy Endpoint Outside the US (Key Secondary Endpoint in the US)

The primary efficacy outside the US (secondary in the US) is by-patient sputum culture conversion monthly through Month 6. The Estimand corresponding to the primary endpoint is defined with the following five attributes:

1. Population: Patients with MAC culture-positive Pre-Study and Screening respiratory specimens

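### Phase 3 collects each continuous PRO twice before dosing, but its efficacy models adjust for only one of the two scores: a missed efficiency of modest and uncertain size, not an error

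*SAP*

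**What the plan says.** Protocol 7.5.5 has the four instruments and PGIS completed twice before dosing, "once between Days -14 and -7 and on Day 1 prior to study drug administration) to assess test-retest reliability". The schedule in Appendix A covers both parts of the study ("Table 3: Schedule of Assessments: Screening through Month 6 (Phases 2 and 3"). The repeat is there for reliability: "PRO test-retest reliability will be assessed in Phase 2 and may be analyzed in Phase 3 if deemed necessary". SAP 2.2.1 gives the same purpose: "The QOL-B, NTM Symptoms Module, SGRQ-C, and PGIS will also be completed during Screening for test-retest reliability assessment".

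SAP 3.1.2 and the estimand in SAP 3.4.3.1 define the PRO baseline as the patient's last entry, in a window that closes one day after first dose. The Phase 3 models then use that single score:

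- **US primary endpoint (SAP 3.4.3.1):** "Change from baseline to Month 6 in QOL-B respiratory domain score will be analyzed using an analysis of covariance (ANCOVA) model, including baseline score", together with treatment and the two stratification factors.
- **Other continuous PROs (SAP 3.4.3.3):** change "will be analyzed using an analysis of covariance (ANCOVA) model, including baseline score, treatment and stratification factors". This includes the MACrO2 total scaled score, which is second in the US testing order.
- **Exploratory MMRM (SAP 3.4.3.4):** the corresponding baseline score as the only continuous covariate.

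No Phase 3 efficacy model uses both pre-dose scores.

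**The concern.** A single PRO score contains week-to-week noise, which weakens it as a covariate. QOL-B has a one-week recall (Protocol 7.5.5.2), and the two completions are at least a week apart, so they largely describe different weeks. A second score taken before randomization may therefore predict Month 6 beyond what Day 1 predicts. If it does, adjusting for both reduces the residual variance of the US primary endpoint and of the second-ranked endpoint without new data.

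Precision matters here because the trial was terminated early (SAP Sections 1 and 3.4). Phase 3 cannot regain it by enrolling more patients.

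**Working it through.** **The plan's own figure.** SAP 2.2.7 gives about 90% power for 124 versus 62 patients, 30% versus 10%, two-sided alpha 0.05. The pooled normal formula gives 89.7%, and exact enumeration of the Miettinen-Nurminen score test gives 90.7%, so the figure reproduces. For 20% exclusions, 186/0.8 = 232.5, against 234 planned. These figures belong to the binary endpoint that has been replaced. The SAP states no power, SD or sample size for QOL-B change.

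**Inputs for the gain (all assumed, since the documents give none):**
- rho: correlation of the Day 1 score with the Month 6 score, 0.5-0.6.
- tau: correlation between the two pre-dose scores, 0.7-0.8.
- k: correlation of Screening with Month 6, as a fraction of rho.

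**Formula.** With Day 1 as a covariate, modelling change or the Month 6 score gives the same residual variance, proportional to 1 - rho^2. Adding Screening raises R-squared by rho^2 (k - tau)^2 / (1 - tau^2). The proportional reduction in residual variance is therefore

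rho^2 (k - tau)^2 / [(1 - tau^2)(1 - rho^2)].

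With k = 1 (equal prediction), the variance ratio is [1 - 2 rho^2/(1 + tau)] / (1 - rho^2).

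Example, rho = 0.5, tau = 0.8, k = 1: 0.25 x 0.04 / (0.36 x 0.75) = 0.010/0.270 = 3.7%. With k = 0.9: 0.25 x 0.01 / 0.27 = 0.9%.

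| rho | tau | k = 1 | k = 0.95 | k = 0.90 | k = tau |
|---|---|---|---|---|---|
| 0.5 | 0.8 | 3.7% | 2.1% | 0.9% | 0 |
| 0.5 | 0.7 | 5.9% | 4.1% | 2.6% | 0 |
| 0.6 | 0.8 | 6.3% | 3.5% | 1.6% | 0 |
| 0.6 | 0.7 | 9.9% | 6.9% | 4.4% | 0 |

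The last column is serial decay: Screening is related to Month 6 only through Day 1.

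**In other units.** For k = 1, confidence intervals are 1.9% to 5.1% narrower. An analysis with 80% power (an assumed base) would have 81.5% to 83.9%. On 186 patients, the gain equals about 7 to 20 more. For k = 0.90, power is 80.4% to 81.7%, and the equivalent is about 2 to 9 patients. The patient counts are illustrative because the analysed Phase 3 number is not stated.

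**Cost of the covariate.** One degree of freedom costs roughly 1/186 = 0.5% of variance at that size, so the smallest gains in the table are nearly cancelled.

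**Simulation.** 20,000 trials at N = 186, rho = 0.5, tau = 0.8, k = 1, adjusting for the mean of the two scores, gave a variance ratio of 0.958 (formula 0.963). Power was 89.8% with one score and 90.8% with both.

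**The case against.** The strongest reply is that nothing is wrong. The SAP defines one baseline and uses it consistently. ANCOVA on that score plus the stratification factors is valid, and the Screening completion has its own stated purpose. All of this stands.

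The second reply is that the gain depends on Screening predicting Month 6 about as well as Day 1 does. For some patients the documents give reason to doubt this. Those whose background regimen had stopped restart it at Screening (Protocol 4.1, criterion 3.d). Those treated for another lung infection need only finish that treatment before randomization (Protocol 4.2, criterion 1). Their state at Days -14 to -7 may differ from Day 1. This also stands, and it is why zero belongs in the range.

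A reader might infer three stronger points that the documents do not support:

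- **The Screening score has no role in Phase 3 efficacy.** Under the last-entry rule it becomes the baseline when no Day 1 entry exists.
- **Day 1 is unusually noisy because patients must report a moderate or worse symptom to qualify.** That criterion concerns MACrO2 symptoms, not the QOL-B respiratory domain. Patients also identify a key symptom at the Day -14 to -7 visit (Protocol 7.5.5.1). Selection before randomization affects both arms alike.
- **A gain is assured.** Over rho 0.4-0.7 and tau 0.7-0.9 the formula with k = 1 gives 1% to 17%, but that range excludes zero only because k = 1 is assumed. The 17% corner needs the correlation with Month 6 to equal the retest correlation over one to two weeks (both 0.7).

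**Conclusion.** The point holds as a missed efficiency. It is neither an error nor a source of bias, and the planned primary analysis needs no correction to be valid. Both scores are collected in Phase 3 and only one is used for adjustment; that much is clear from the documents.

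The size is not. At the assumed correlations, residual variance falls by about 4-10% if the two scores predict Month 6 equally well, by about 1-4% if Screening correlates 10% less, and by nothing if Screening adds no information beyond Day 1. The percentages do not depend on the number analysed. The change is worth making because it is cheap and because it must be prespecified, not because a large gain can be promised.

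**What to change.** Keep change from the SAP-defined baseline to Month 6 as the variable, and leave the population-level summary as it is. Before Phase 3 unblinding, add the Screening (Day -14 to -7) score of the same instrument as an additional covariate in the continuous-PRO ANCOVAs of SAP 3.4.3.1 and 3.4.3.3 and in the MMRM of SAP 3.4.3.4.

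State a rule for a missing pre-dose score. If either is missing, impute that covariate by a prespecified, treatment-blind method, for example a regression of one pre-dose score on the other pooled over arms, so that no patient is dropped. Averaging whatever is available would not serve: when Screening is missing, the average is Day 1 again, and the same value enters twice.

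The sponsor can first estimate the three correlations in Phase 2, which used the same schedule. Those patients are independent of Phase 3, so the reasoning in SAP 3.4 on alpha applies here too.

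The cost is one degree of freedom and a short SAP edit, with no new data. After Phase 3 unblinding the change would have to be documented as a deviation (SAP Section 1).
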